10.1.4 Immune-related adverse events

Based on the mechanism of action of durvalumab and tremelimumab leading to T-cell activation and proliferation, there is a possibility of observing irAEs during the conduct of this study. Potential irAEs may be similar to those seen with the use of ipilimumab, BMS-936558 (anti-PD-1 mAb), and BMS-936559 (anti-PD-L1 mAb) and may include immune-mediated enterocolitis, dermatitis, hepatitis (hepatotoxicity), pneumonitis, and endocrinopathies (Hodi et al 2010, Brahmer et al 2012, **Error! Reference source not found.**). These AEs are inflammatory in nature and can affect any organ. With anti-PD-L1 and anti-CTLA-4 combination therapy, the occurrence of overlapping or increasing cumulative toxicities that include irAEs could potentially occur at higher frequencies than with either durvalumab or tremelimumab monotherapy. Patients should be monitored for signs and symptoms of irAEs. In the absence of an alternate etiology (eg, infection or PD), an immune-related etiology should be considered for signs or symptoms of enterocolitis, dermatitis, pneumonitis, hepatitis, and endocrinopathy. In addition to the dose modification guidelines provided in Table 1, it is recommended that irAEs are managed according to the general treatment guidelines outlined for ipilimumab (**Error! Reference source not found.**). These guidelines recommend the following:

- Patients should be evaluated to identify any alternative etiology.
- In the absence of a clear alternative etiology, all events of an inflammatory nature should be considered immune related.

- Symptomatic and topical therapy should be considered for low-grade events.
- Systemic corticosteroids should be considered for a persistent low-grade event or for a severe event.
- More potent immunosuppressives should be considered for events not responding to systemic steroids (eg, infliximab or mycophenolate).
- If the Investigator has any questions in regards to an AE being an irAE, the Investigator should immediately contact the Study Physician.

10.2 Assessment of safety parameters

10.2.1 Assessment of severity

Assessment of severity is one of the responsibilities of the investigator in the evaluation of AEs and SAEs. Severity will be graded according to the NCI CTCAE v4.03.

The determination of severity for all other events not listed in the CTCAE should be made by the investigator based upon medical judgment and the severity categories of Grade 1 to 5 as defined below.>>

Grade 1 (mild)	An event that is usually transient and may require only minimal treatment or therapeutic intervention. The event does not generally interfere with usual activities of daily living.
Grade 2 (moderate)	An event that is usually alleviated with additional specific therapeutic intervention. The event interferes with usual activities of daily living, causing discomfort but poses no significant or permanent risk of harm to the subject.
Grade 3 (severe)	An event that requires intensive therapeutic intervention. The event interrupts usual activities of daily living, or significantly affects the clinical status of the subject.
Grade 4 (life threatening)	An event, and/or its immediate sequelae, that is associated with an imminent risk of death or with physical or mental disabilities that affect or limit the ability of the subject to perform activities of daily living (eating, ambulation, toileting, etc).
Grade 5 (fatal)	Death (loss of life) as a result of an event.

It is important to distinguish between serious criteria and severity of an AE. Severity is a measure of intensity whereas seriousness is defined by the criteria in Section 9.2.1. A Grade 3 AE need not necessarily be considered an SAE. For example, a Grade 3 headache that persists for several hours may not meet the regulatory definition of an SAE and would be considered a nonserious event, whereas a Grade 2 seizure resulting in a hospital admission would be considered an SAE.

10.2.2 Assessment of relationship

An investigator who is a qualified provider will evaluate all adverse events according to the NCI Common Terminology for Adverse Events (CTCAE), version 4.03. Any adverse event which

changes CTCAE grade over the course of a given episode will have each change of grade recorded on the adverse event case report forms/worksheets.

All adverse events regardless of CTCAE grade must also be evaluated for seriousness.

The determination of the likelihood that durvalumab and/or tremelimumab caused the adverse event will be provided by an investigator who is a qualified physician. The investigator's signed/dated initials on the source document or worksheet that supports the causality noted on the AE form, ensures that a medically qualified assessment of causality was done. This initialed document must be retained for the required regulatory time frame. The criteria below are intended as reference guidelines to assist the investigator in assessing the likelihood of a relationship between the test drug and the adverse event based upon the available information.

The following components are to be used to assess the relationship between durvalumab and/or tremelimumab and the AE; the greater the correlation with the components and their respective elements (in number and/or intensity), the more likely that durvalumab and/or tremelimumab caused the adverse event (AE):

- Is there evidence that the subject was actually exposed to durvalumab and tremelimumab such as: reliable history, acceptable compliance assessment expected pharmacologic effect, or measurement of drug/metabolite in bodily specimen?
- Did the AE follow in a reasonable temporal sequence from administration of durvalumab and tremelimumab?
- Is the time of onset of the AE compatible with a drug-induced effect (applies to trials with investigational medicinal product)?
- Is the AE not reasonably explained by another etiology such as underlying disease, other drug(s)/vaccine(s), or other host or environmental factors

10.3 Recording of adverse events and serious adverse events

Adverse events will be recorded using a recognized medical term or diagnosis that accurately reflects the event. Adverse events will be assessed by the investigator for severity, relationship to the investigational product, possible etiologies, and whether the event meets criteria of an SAE and therefore requires immediate notification to AstraZeneca/MedImmune Patient Safety.

The following variables will be collected for each AE:

- AE (verbatim)
- The date when the AE started and stopped
- Changes in NCI CTCAE grade and the maximum CTC grade attained
- Whether the AE is serious or not
- Investigator causality rating against durvalumab or tremelimumab (yes or no)

- Action taken with regard to durvalumab + tremelimumab/comparator/combination agent
- Outcome
-

In addition, the following variables will be collected for SAEs as applicable:

- Date AE met criteria for serious AE
- Date of hospitalization and discharge, if applicable
- Date of death and probable cause, if applicable
- Autopsy performed
- Description of AE
- Causality assessment in relation to Study procedure(s)
- Causality assessment in relation to palliative hypofractionated radiation therapy

Events, which are unequivocally due to disease progression, should not be reported as an AE during the study.

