11.2 Methods of statistical analyses

11.2.1 Safety Analyses

Safety and tolerability is the primary endpoint of this study, and all patients enrolled (including those replaced in the run in phase) will be assessed for this endpoint. Adverse events will be recorded and graded based on CTCAE v. 4, and their relationship to the experimental agents reported.

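### Radiation causality is prespecified for serious adverse events only, so a non-serious radiation toxicity can be reported simply as not drug-related

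*Combined protocol and SAP*

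**What the plan says.** Section 10.3 sets out two lists of variables. The first opens with "The following variables will be collected for each AE" and holds the term, dates, grade, seriousness, action taken, outcome and a single causality item: "Investigator causality rating against durvalumab or tremelimumab (yes or no". The second opens with "In addition, the following variables will be collected for SAEs as applicable", and only there does one find "Causality assessment in relation to palliative hypofractionated radiation therapy".

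The lead-in to Section 10.3 is somewhat wider: "Adverse events will be assessed by the investigator for severity, relationship to the investigational product, possible etiologies". Possible etiologies are thus to be considered for every event, but they are not among the listed variables and radiation is not named.

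Section 10.2.2 governs the judgement of relationship: "The determination of the likelihood that durvalumab and/or tremelimumab caused the adverse event will be provided by an investigator who is a qualified physician". Its criteria concern the drugs throughout. Section 3.3, however, refers the reader to 10.2.2 for guidance on attributing toxicity to the drug and radiation combination.

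Section 10.2.1 separates severity from seriousness: "A Grade 3 AE need not necessarily be considered an SAE". Section 6.4 says that monitored events will include possible radiation toxicities. Section 11.2.1, the primary safety analysis, has events graded and "their relationship to the experimental agents reported".

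**The concern.** The regimen under test has three components and radiation is one of them. The primary objective is the safety of all three together, in a single arm with no concurrent control. When an event is non-serious, the only prespecified causality record is a yes/no for the drugs.

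The last criterion in Section 10.2.2 makes this worse than a blank field. It asks whether the event lacks another reasonable explanation, and an event well explained by radiation has one. An investigator following the text can therefore enter no for drug, the same code as for an intercurrent illness. Section 11.2.1 would then show the event as unrelated to the agents, although a component of the study regimen may have caused it.

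Such toxicity is not remote here. Section 1.1.5 cites morbidity of 10-50% for SBRT re-irradiation, and Section 4.1 admits previously irradiated sites after an interval of more than 6 months. At stake is a readable account of which component caused the non-serious toxicity.

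**Working it through.** **1. The plan's own figures, to see whether the gap touches them (Section 11.3).**
- Half-width of the 95% interval at n = 20 and p = 0.5: 1.96 × √(0.5 × 0.5 / 20) = 0.219. The plan states 22%, so it reproduces.
- Chance of seeing at least one event at 10% prevalence: 1 − 0.90^20 = 0.878. The plan states at least 87%, so it reproduces.

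Both are statements about the rate of a toxicity in 20 patients. Neither uses a causality rating, so neither changes.

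**2. The sections side by side.**

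| Question | Non-serious AE, any grade | SAE |
|---|---|---|
| Recorded and graded? | Yes (10.3, 11.2.1) | Yes |
| Drug causality variable? | Yes, yes/no (10.3) | Yes |
| Radiation causality variable? | None listed | Yes (10.3) |
| Criteria for drug attribution? | Yes (10.2.2) | Yes |
| Criteria for radiation attribution? | None (10.2.2), though 3.3 says they are there | None |

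Section 10.2.1 shows that the first column is not confined to mild events, because Grade 3 events can fall in it. No other section supplies a radiation-causality variable for non-serious events.

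**3. Scale (illustration only).** Section 11.3 cites a Grade 3 or higher rate of 6-16% for SBRT with the antibody.
- Expected patients with any such event: 20 × 0.06 = 1.2 and 20 × 0.16 = 3.2.
- These totals include drug-related events and SAEs, and the SAEs already have the radiation field. They are not a count of affected patients.
- The documents do not give the non-serious share. Assume 25% to 75%, and assume that every one of these events could be radiation-related. Expected patients without a radiation rating are then 1.2 × 0.25 = 0.3 at the low end and 3.2 × 0.75 = 2.4 at the high end.
- Chance of at least one such patient: 1 − (1 − 0.06 × 0.25)^20 = 1 − 0.985^20 = 26% at the low end, and 1 − (1 − 0.16 × 0.75)^20 = 1 − 0.88^20 = 92% at the high end.

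The breadth of that range shows how little the documents settle the size. Non-serious Grade 1-2 radiation toxicity also lacks the variable, and the documents give no rate for it.

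**The case against.** The strongest reply is that the primary analysis does not need event-level attribution to radiation. Section 11.3 judges the increase in toxicity by the upper confidence bound on the toxicity rate, and the synopsis summarises patients by type of toxicity. Every event is counted and graded whatever its cause. This stands. A reader might infer that the effect of adding radiation on toxicity cannot be assessed from the data, but the documents do not support that: the comparison they define rests on the overall rate and is untouched.

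A second reply is that attribution is not impossible. Possible etiologies are considered for every event, a source document supporting the drug judgement is retained, terms and dates are collected, and radiation is one short course to known lesions. This also stands, so it would be too strong to say that non-serious toxicity cannot be attributed to radiation. What is missing is a prespecified variable and criterion. Chart review after the fact is possible but less reliable than prospective recording.

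Third, Section 10.3 says that events unequivocally due to progression are not to be reported as AEs, so a no for drug is less ambiguous than it first looks. That is partly right. Equivocal cases and all other causes still share the code with radiation.

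Fourth, Table 8 lists only the two drugs as investigational products, so the experimental agents of Section 11.2.1 may mean the drugs alone, and collection would then match the planned report. The cover page lists radiation with the study substances, which leaves the term open. Even on the narrow reading, the cross-reference in Section 3.3 remains unfulfilled.

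Finally, the case report form is not in the documents and may already hold the field. The point concerns the variables that the protocol prespecifies.

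**Conclusion.** The gap is real and limited. The protocol prespecifies radiation causality for SAEs only and gives criteria for drug attribution only, contrary to what Section 3.3 says of Section 10.2.2. A non-serious in-field toxicity, including one of Grade 3, can appear in the primary safety report as not drug-related, with nothing prespecified to separate it from other causes.

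The gap affects attribution, not counting. Overall toxicity rates, N = 20, the 22% precision and the Section 11.3 comparison stand. The drug-related count used by the stopping rule in Section 3.3 also still has its input, because the drug rating is collected for every event.

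A reader might take 1 to 3 of 20 patients as the number affected. The documents do not support that, since the 6-16% rate covers all Grade 3 or higher toxicity. The number affected at Grade 3 or higher is an unknown subset of the 1.2 to 3.2 expected at that rate. The range of 0.3 to 2.4 rests on the assumed non-serious share of 25-75% and on treating all such events as possibly radiation-related. The change is worth making mainly because it is cheap and the trial has no control arm.

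**What to change.** - In Section 10.3, move the existing radiation-causality item from the SAE list to the list for each AE.
- In Section 10.2.2, add radiation to the attribution criteria so that the section delivers what Section 3.3 says it contains. State that drug and radiation are rated separately and that both may be yes.
- In Section 11.2.1, tabulate Grade 3 or higher events as drug-related, radiation-related, both or neither.

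The cost is one more field per AE, one paragraph and one table. There are no added visits and no change to the sample size.

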10.3.1 Study recording period and follow-up for adverse events and serious adverse events

Adverse events and serious adverse events will be recorded from time of administration of the first dose of investigational drug, throughout the treatment period and including the follow-up period (90 days after the last dose of durvalumab + tremelimumab).

During the course of the study all AEs and SAEs should be proactively followed up for each subject. Every effort should be made to obtain a resolution for all events, even if the events continue after discontinuation/study completion.

If a subject discontinues from treatment for reasons other than disease progression, and therefore continues to have tumor assessments, drug or procedure-related SAEs must be captured until the patient is considered to have confirmed PD and will have no further tumor assessments.

The investigator is responsible for following all SAEs until resolution, until the subject returns to baseline status, or until the condition has stabilized with the expectation that it will remain chronic, even if this extends beyond study participation.

Follow-up of unresolved adverse events

Any AEs that are unresolved at the subject's last visit in the study are followed up by the investigator for as long as medically indicated, but without further recording in the CRF. After 90 days, only subjects with ongoing investigational product-related SAEs will continue to be followed for safety.

AstraZeneca/MedImmune retains the right to request additional information for any subject with ongoing AE(s)/SAE(s) at the end of the study, if judged necessary.

Post study events

After the subject has been permanently withdrawn from the study, there is no obligation for the investigator to actively report information on new AE or SAEs occurring in former study subjects after the 90-day safety follow-up period for patients treated with durvalumab + tremelimumab. However, if an investigator learns of any SAEs, including death, at any time after the subject has been permanently withdrawn from study, and he/she considers there is a reasonable possibility that the event is related to study treatment, the investigator should notify the study sponsor and AstraZeneca/MedImmune Drug Safety.

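### Section 10.3.1 gives conflicting rules on which SAEs are followed after 90 days, leaves SAEs due only to radiation uncertain, and stops CRF recording of events still open at the last visit

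*Combined protocol and SAP*

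**What the plan says.** Section 10.3.1 contains five statements that bear on each other.

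- AEs and SAEs are recorded from the first dose "throughout the treatment period and including the follow-up period (90 days after the last dose of durvalumab + tremelimumab").
- For SAEs of any cause: "The investigator is responsible for following all SAEs until resolution, until the subject returns to baseline status, or until the condition has stabilized". The sentence goes on to say that this holds beyond study participation.
- For patients who stop treatment for a reason other than progression, "drug or procedure-related SAEs must be captured until the patient is considered to have confirmed PD and will have no further tumor assessments".
- AEs unresolved at the last study visit "are followed up by the investigator for as long as medically indicated, but without further recording in the CRF".
- The next sentence reads: "After 90 days, only subjects with ongoing investigational product-related SAEs will continue to be followed for safety".

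Two other sections define what is collected. Section 10.2.2 says that an event that "changes CTCAE grade over the course of a given episode will have each change of grade recorded" on the case report forms or worksheets. Section 10.3 lists among the variables for each AE "Changes in NCI CTCAE grade and the maximum CTC grade attained", together with the stop date and outcome.

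The investigational products in Table 8 (Section 15.1) and in the synopsis entry on product and dose are durvalumab and tremelimumab only. Section 14 makes the CRF the source for analysis. Section 11.2.1 makes safety and tolerability the primary endpoint and gives no time cut-off for the maximum grade.

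**The concern.** The all-SAE rule and the 90-day sentence cannot both be followed for an SAE attributed only to radiation that is still open after 90 days. Radiation is the component that makes this combination new: the synopsis says that the triplet has not been studied before. Section 1.1.5 cites morbidity of 10-50% and mortality of 1-5% for stereotactic re-irradiation, and inclusion criterion 6 admits previously irradiated sites after more than 6 months. Follow-up of radiation-related SAEs should not depend on which sentence site staff happen to read.

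The second issue is the gap between following and recording. Section 10.1.1 uses AE for serious and non-serious events alike, so the sentence that ends CRF recording covers SAEs too. An investigator may know that an open event worsened, or how it ended, while the analysis file keeps the last in-study grade and an unknown outcome. Any resulting error in the maximum grade runs one way: the recorded grade can be too low but not too high.

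**Working it through.** **1. The plan's own figures.** Section 11.3 states precision within 22 points and at least an 87% chance of seeing a toxicity of 10% prevalence, with 20 patients.

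- Half-width: 1.96 × √(0.5 × 0.5 / 20) = 0.219.
- Detection: 1 − 0.90^20 = 0.878.

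Both reproduce. Neither uses length of follow-up, so they neither support nor refute the point.

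**2. Which rule covers an ongoing SAE due only to radiation?**

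| Statement in 10.3.1 | Covers it? |
|---|---|
| All SAEs to resolution, baseline or stabilisation | Yes, for follow-up; silent on the CRF |
| Drug- or procedure-related SAEs until confirmed PD | Unclear: Section 10.3 lists study procedures and radiation as separate causality items. Applies only to patients who stopped for reasons other than progression |
| After 90 days, product-related SAEs only | No, given Table 8 |
| Events open at the last visit | Followed, but not recorded further |

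**3. When recording ends.** Inputs: radiotherapy starts 2 weeks after the first dose (synopsis), taken as day 15; Q4W dosing; AE window to 90 days after the last dose (Section 10.3.1); stopping-rule window to 30 days after the last infusion (Section 3.3). The last dose at cycle k falls on day 28(k − 1) + 1.

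| Last cycle given | Last dose, day | AE window ends, day | Days after radiotherapy start | Stopping-rule window ends, day |
|---|---|---|---|---|
| 1 | 1 | 91 | 76 | 31 |
| 2 | 29 | 119 | 104 | 59 |
| 4 | 85 | 175 | 160 | 115 |
| 13 | 337 | 427 | 412 | 367 |

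The stopping-rule window closes 90 − 30 = 60 days before the AE window in every row. The DLT window (28 days in Section 6.4; 8 weeks, or 56 days, in the synopsis and Section 3.3) closes before day 91 even after a single dose. Those rules lose data only if the last visit comes before their windows close. The exposed part is the descriptive toxicity table, mainly for patients who stop early.

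**4. Possible size (assumptions only).** The documents give no rate of late worsening. Suppose that 5% to 30% of patients with a Grade 3-4 event first reach that grade after recording stops.

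- A true 17% (the reference rate in Section 11.3) is recorded as 17% × 0.95 = 16.2% down to 17% × 0.70 = 11.9%. In 20 patients that is 3.4 × 0.05 = 0.17 to 3.4 × 0.30 = 1.0 patients missed.
- If the same share of patients with a 10%-prevalence toxicity went unrecorded, detection would be 1 − 0.905^20 = 86.4% down to 1 − 0.930^20 = 76.6%.
- If one patient's Grade 2 event became Grade 3 after the last visit, with no other Grade 3 event in that patient, 3/20 would be recorded in place of 4/20. The exact 95% upper limits are 37.9% and 43.7%, a difference of 5.8 points in the quantity on which Section 11.3 bases its conclusion.

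A Grade 3 event that later becomes Grade 4 would not change a Grade 3 or higher rate at all.

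**The case against.** A reader might infer that radiation-related SAEs are dropped after 90 days. The documents do not support that. The all-SAE rule has no causality limit, Section 10.3 requires radiation causality for every SAE, and Section 10.3.1 asks for notification of SAEs learned of later that may be related to study treatment. What stands is a contradiction, not a rule of omission.

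A reader might also infer that the maximum grades behind the primary endpoint are generally cut short, or that the stopping rule is compromised. Neither follows. Only an event that began in the window, was still open at the last visit and worsened afterwards is affected. Appendices 2 and 3 schedule AE/SAE assessment at day 30 and months 2 and 3, so the DLT and stopping-rule windows normally close first. They might not for a patient who starts new therapy early: Section 6.1.1 then brings the 30-day safety visit forward and moves the patient to survival follow-up.

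It can further be said that Sections 10.2.2 and 10.3 list variables while Section 10.3.1 sets the collection period, and that maximum grade within a fixed period is a coherent quantity. That is fair, but the plan nowhere declares this as its definition. It does not define the last study visit relative to the 90-day window, or say what the 90 days in the restrictive sentence run from.

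Finally, open-ended recording of every AE would collect chronic low-grade events, and grade changes confounded by later therapy. This stands, and it limits the fix.

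**Conclusion.** The point holds as an internal inconsistency in Section 10.3.1 with a limited effect on data completeness. SAEs due only to radiation are subject to two incompatible follow-up rules, and the maximum grade and outcome of events open at the last visit may be incomplete in the toxicity table. This rests on reading investigational product as Table 8 and the synopsis define it; the title page sets radiation beside the two drugs, which adds to the ambiguity.

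No bias in the primary endpoint has been shown. Its size cannot be derived from the documents, and under the assumed range above it is at most about one patient in 20, well inside the stated precision of 22 points. The reasons to act are that any error goes in one direction, that it concerns the component under test, and that the correction is nearly free.

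**What to change.** 1. In Section 10.3.1, reconcile the 90-day sentence with the all-SAE rule, so that it covers SAEs related to durvalumab, tremelimumab or radiation. State what the 90 days run from, and define the last study visit relative to the recording window.
2. For SAEs, and for Grade 3 or higher AEs related to study drug or radiation, with onset in the recording window, require the CRF to be updated with grade changes, maximum grade and outcome until the event resolves, returns to baseline or stabilises.
3. In Section 11.2.1, state the cut-off used for the maximum grade of all other AEs.

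Step 2 needs a radiation causality item for non-serious Grade 3 or higher AEs, because Section 10.3 now collects it for SAEs only. Otherwise the cost is wording and a few late CRF entries for patients whom the investigator is already following.
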